DSMB	Data and Safety Monitoring Board
FFR	Federal Financial Report
FWA	Federalwide Assurance
GAE	Genicular Artery Embolization
GCP	Good Clinical Practice
HIPAA	Health Insurance Portability and Accountability Act
ICF	Informed Consent Form
ICH	International Conference on Harmonisation
IRB	Institutional Review Board
ISM	Independent Safety Monitor
KOOS	Knee Injury and Osteoarthritis Outcome Score
MRA	Magnetic Resonance Angiogram
MOP	Manual of Procedures
N	Number (typically refers to participants)
NIH	National Institutes of Health
OA	Osteoarthritis
OHRP	Office for Human Research Protections
OHSR	Office of Human Subjects Research
PI	Principal Investigator
QA	Quality Assurance
QC	Quality Control
QOL	Quality of Life
SAE	Serious Adverse Event/Serious Adverse Experience
SOP	Standard Operating Procedure
TKA	Total Knee Arthroplasty
US	United States
VAS	Visual Analogue Scale

Protocol Summary

Title	Prospective pilot study on geniculate artery embolization for treatment of persistent knee pain post total knee arthroplasty
Short Title	Geniculate artery embolization for post TKA pain
Brief Summary	Single-arm, single-center, no sham or placebo, prospective pilot trial designed to evaluate the safety and efficacy of transcatheter arterial embolization in patients with persistent knee pain resistant to conservative management for at least 9 months after total knee arthroplasty (TKA). Eligible participants will receive geniculate artery embolization (GAE) using Embozene™ Color-Advanced Microspheres. Patients will be followed up for a total of 24 months after GAE.
Phase	Pilot study
Objectives	
Primary objective: to determine the effectiveness of GAE in reducing knee pain at 6-months post GAE in patients with persistent knee pain after TKA. This will be assessed by evaluating the clinical success rate defined as at least 15% improvement in Knee injury and Osteoarthritis Outcome Score (KOOS) pain score from baseline to follow-up visit at 6 months post-intervention without an increase in baseline incidence of pain medication use or intra-articular injections.
 
Secondary objectives:
 
 - To evaluate the safety of GAE - To determine feasibility and technical success of GAE - To determine whether GAE improves knee symptoms and quality of life (QOL) - To determine the effect of GAE on disease-specific biomarkers in the blood, urine, and synovial fluid of the target knee
Methodology	Prospective, single-arm (no sham or placebo), single-center
Endpoint	
Primary Efficacy endpoint: KOOS pain score at 6-months post intervention
 
Secondary endpoints:
 
 - Rate, type, causality, and severity of adverse events (AEs) - KOOS scores at 3-, 6-, 12-, and 24-month visits - QOL index value at 3-, 6-, 12-, and 24-month visits - Pain visual analog scale (VAS) at 3-, 6-, 12-, and 24-month visits - Magnetic Resonance Angiogram (MRA) findings at 6 and 24-month visits
Study Duration	4 years
Participant Duration	Each individual subject will be enrolled for approximately 25 months to complete all study visits from the initial screening visit to last follow up at 24-months post intervention
Population	40 patients, age 30-85, of any gender, with knee pain resistant to conservative management for at least 9 months post TKA.
Study Sites	NYU Langone Health Hospitals
Number of participants	Data from 40 patients who complete 6-month visit will be required The study would enroll 50 patients to account for an attrition rate of 20%
Description of Study Agent/Procedure	Embozene™ Color-Advanced Microspheres are spherical, tightly calibrated, biocompatible, non-resorbable, hydrogel microspheres coated with an inorganic perfluorinated polymer used for embolization.
Key Procedures	GAE; a transcatheter arterial embolization of one or more genicular artery(ies) using Embozene™ Color-Advanced Microspheres

Statistical Analysis	
The primary objective is to assess the clinical success rate, which will be summarized in terms of the observed proportion of patients manifesting a positive response and a two-sided exact 95% confidence interval (CI) per the Blyth-Still-Casella method. The treatment will be declared a success if the data support the conclusion that at least 75% of treated patients show a positive response.
 
Preliminary analysis will be performed after 25% (10 subjects) of study sample size complete the 6-month follow-up visit.

----------------------	---

Schematic of Study Design

1 Introduction, Background Information and Scientific Rationale

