2.1 Primary Objective

The primary objective of the study is to determine the effectiveness of GAE in reducing knee pain at 6-month post intervention. This will be assessed by evaluating the clinical success rate defined as at least 15% improvement of KOOS pain score from baseline to follow-up visit at 6 months post GAE without an increase in baseline incidence of analgesics [59].

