3.1 Description of Study Design

This study is a single-center, single arm, no sham or placebo, open label, prospective pilot study designed to evaluate the safety and feasibility of GAE for the treatment of knee OA resistant to conservative management for at least 9 months post TKA. Enrolled patients will receive angiography and embolization of the one or more geniculate arteries in the affected knee using 100 μ m Embozene microspheres. If both knees are affected and fit eligibility criteria, the knee with the higher pain score on electronic VAS will be targeted.

The primary objective is to evaluate the effectiveness of GAE in reducing knee pain at 6 months. The primary objective will be evaluated by the clinical success rate. Clinical success is defined as at least 15% improvement in KOOS pain score at 6-month post GAE without increase in baseline use of analgesics. 40 patients will be required for this study to evaluate the primary outcome (complete 6-month visit). The study would accrue 50 patients to account for an attrition rate of 20%.

Change in KOOS pain score and VAS pain will be used as a measure of efficacy (i.e., pain reduction). KOOS questionnaire is a widely used, disease-specific measure. It was developed as an extension of the WOMAC score with the purpose of evaluating short-term and long-term symptoms and function in subjects with knee injury and osteoarthritis [60]. Specifically, the KOOS questionnaire assesses 5 domains: knee pain, knee symptoms/stiffness, knee function (activities of daily living), knee function (sports/recreational activities), and knee related quality of life.

The electronic VAS is a horizontal line with no markings on the scale except "No pain" on the left (score: 0 mm) and "worst possible pain" on the right end of the scale (score: 100 mm). Subjects mark the VAS to indicate their current pain level, with 0 mm representing "No pain" and 100 mm representing "worst possible pain". In our study, subjects will be asked to mark their pain level on a paper VAS on study questionnaire form and will give a score between 0 to 100, which will be documented on the appropriate eCRF.

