4.2 Exclusion Criteria

An individual who meets any of the following criteria will be excluded from participation in this study:

1. Active systemic or local knee[#] infection
2. Active malignancy
3. Life expectancy less than 6 months
4. Prior ipsilateral knee arthroscopic surgery or repeat TKA (within 9 months of screening)
5. Ipsilateral knee intra-articular injection in the last 3 months
6. Rheumatoid arthritis, spondyloarthropathies, crystal disease, gout, pseudogout, or lupus
7. Pregnant during the study period
8. Renal dysfunction as defined by serum creatinine >1.6 dl/mg or eGFR <60 on blood tests obtained within 30 days of procedure
9. Body weight greater than 200 Kg
10. Known history of severe contrast allergy to iodinated contrast resulting in anaphylaxis
11. Known significant arterial atherosclerosis that would limit selective angiography and/or lower extremity symptoms thought to be secondary to arterial vascular disease (eg claudication, ischemic rest pain)
12. Known avascular necrosis in the target knee
13. Complications of TKA such as suspected or confirmed early loosening, ligamentous instability, reflex sympathetic dystrophy, polyethylene wear with or without particle disease (osteolysis), patellofemoral mal-tracking, referred hip and low back pain, and large effusions** (with or without hemarthrosis) on available imaging studies such as knee radiographs, computed tomography scans, and / or the MRA performed for the study purposes.
14. Patient is enrolled in a different trial for treatment of knee pain post total knee arthroplasty (ipsilateral knee)

using Musculoskeletal Infection Society (MSIS) criteria for diagnosis of prosthetic joint infection

2011 Musculoskeletal Infection Society (MSIS) criteria ^[1]	
PJI is present when 1 major criteria exist or 4 out of 6 minor criteria exist	
Major criteria:	
	
 ■ 2 positive periprosthetic cultures with phenotypically identical organisms ■ A sinus tract communicating with the joint
Minor criteria:	
	
 ■ Elevated CRP and ESR ■ Elevated synovial fluid WBC count or ++ change on leukocyte esterase test strip ■ Elevated synovial fluid PMN% ■ Presence of purulence in the affected joint ■ Positive histologic analysis of periprosthetic tissue ■ A single positive culture

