6.1 Study Procedures/Evaluations

6.1.1 Study Specific Procedures

- Imaging assessment with knee MRA (visits 2, 6, and 8):
 - Baseline and follow-up (at 6 and 24 months) knee MRA will be performed.
- Biological specimen collection (visits 2, 5, 6, 7, and 8):
 - Baseline and follow-up biomarker analysis from blood, urine, and knee aspirate (synovial fluid) will be obtained from participants.
- Administration of questionnaires or other instruments for patient-reported outcomes (visits 2, 5, 6, 7, and 8):
 - VAS questionnaire
 - KOOS questionnaire
 - Self-reported quality of life EQ-5D-5L questionnaire
 - Anchor pain questionnaire
- GAE procedure (visit 3)
- Medical history (visits 2, 5, 6, 7, and 8):
 - Complete medical history will be obtained from medical records if available and/or by interview during clinic visits.
- History of previous and concomitant treatment (visits 2, 5, 6, 7, and 8):
 - Knee injections and frequency
 - Medication history. Will focus on medications currently taken for the treatment of knee pain; including prescription and over-the-counter medications for pain.
 - Physical therapy and frequency
 - Weight loss / gain
- Focused physical examination (visits 2, 5, 6, 7, and 8):
 - Vital signs (temperature, blood pressure, heart rate, oxygen saturation, height, weight, BMI)
 - Focused knee examination.

Note: A discussion of the results of any study specific procedures (e.g., radiographic or other imaging or laboratory evaluations) will be provided to participant after the completion of the study unless this information represents a significant health-related issue.

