6.3.4.2 Follow up visit at 3-month (Visit 5, Day 90 ± 10 days)

- Obtain medical history
- Record adverse events as reported by participant or observed by investigator (if applicable)
- Targeted physical exam
- Administration of study questionnaires
- Previous / concomitant treatments, including medical history
- Biospecimen collection (including knee aspiration for synovial fluid collection)

6.3.4.3 Follow up visit at 6 months (Visit 6, Day 180 ± 20 days)

- Obtain medical history
- Record adverse events as reported by participant or observed by investigator (if applicable)
- Targeted physical exam
- Administration of study questionnaires
- Previous / concomitant treatments, including medical history
- Biospecimen collection (including knee aspiration for synovial fluid collection)
- Follow-up knee MRA

6.3.4.4 Follow up visit at 12 months (Visit 7, Day 360 ± 30 days)

- Obtain medical history
- Record adverse events as reported by participant or observed by investigator (if applicable)
- Targeted physical exam
- Administration of study questionnaires
- Previous / concomitant treatments, including medical history
- Biospecimen collection (including knee aspiration for synovial fluid collection)

6.3.4.5 Follow up visit at 24 months (Visit 7, Day 720 ± 40 days)

- Obtain medical history
- Record adverse events as reported by participant or observed by investigator (if applicable)
- Targeted physical exam
- Administration of study questionnaires
- Previous / concomitant treatments, including medical history
- Biospecimen collection (including knee aspiration for synovial fluid collection)
- Follow-up knee MRA

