6.6 Prohibited Medications, Treatments, and Procedures

Not applicable.

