9.2 Statistical Hypotheses

This is a single arm study (i.e., no sham, placebo or alternative treatment included). The primary objective (clinical success rate) is a binary assessment of whether or not each patient achieved clinical success at 6 months post intervention.

The study is designed to test the null hypothesis (H_0) that the true proportion (PT) of patients that will manifest a positive treatment response, is no greater than 0.5 against the one-sided alternative hypothesis (H_A) that $PT \geq 0.75$.

The response rate will be summarized in terms of the observed proportion of patients manifesting a positive response and a two-sided exact 95% confidence interval (CI) per the Blyth-Still-Casella method (31). The treatment will be declared a success if the data support the conclusion that at least 75% of treated patients can be expected to show a positive response. The treatment will be considered unworthy of additional study without further

development if the data are consistent with the conclusion that no more than 50% of treated patients can be expected to show a positive response.

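### The baseline KOOS must be free of recent knee injection but the 6-month KOOS need not be, so clinical success can include a patient re-injected shortly before that visit

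*Combined protocol and SAP*

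**What the plan says.** - **Entry.** Section 4.2, exclusion 5: "Ipsilateral knee intra-articular injection in the last 3 months".
- **Clinical success, three wordings.** All require at least a 15% improvement in KOOS pain at 6 months. The Protocol Summary adds "without an increase in baseline incidence of pain medication use or intra-articular injections". Section 2.1 adds "without an increase in baseline incidence of analgesics". Section 3.1 adds "without increase in baseline use of analgesics". Only the Summary mentions injections.
- **Primary assessment.** Section 6.3.4.3 sets the 6-month visit at Day 180 ± 20 and attaches no injection-free interval.
- **Treatment during follow-up.** Section 6.6, "Prohibited Medications, Treatments, and Procedures", is marked not applicable, so nothing rules out a knee injection after the procedure.
- **Data.** Section 6.1.1 collects "Knee injections and frequency" at visits 2, 5, 6, 7 and 8. It names neither injection dates nor a look-back period.
- **Analysis.** Section 9.4.2 analyses clinical success as a binary outcome. Section 9 does not say how an injection after the procedure is handled, and section 9.1 says no formal SAP will be written.

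**The concern.** The primary result is a before/after responder proportion in one unblinded arm. Its interpretation depends on the two KOOS measurements being taken under comparable conditions, because no control group can absorb the effect of another treatment. The protocol treats recent injections as relevant: it excludes them at entry, records them during follow-up and names them in the Summary definition. Yet it does not require the 6-month score to be as clear of an injection as the baseline score.

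To the extent that an injection relieves pain, a repeat injection before month 6 can carry a patient over the 15% threshold. From a baseline of 40 that threshold is 0.15 × 40 = 6 points. The patient would then be counted in the tested endpoint as a success of embolization.

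**Working it through.** **1. Two hypothetical patients scored under each wording**

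Assumed scores: KOOS pain 40 at baseline and 47 at 6 months, taking a higher score as better. Gain = (47 − 40)/40 = 17.5%, above 15%. Analgesic use is unchanged in both.

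- *Patient 1* had an injection about every 6 months, the last one 4 months before screening, so exclusion 5 is passed. One injection is given at month 5 after the procedure.
- *Patient 2* had no earlier injections and has one at month 5.

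Screening is at most 30 days before the procedure (section 6.3.1), so Patient 1's last injection falls 4 to 5 months before it. That is one injection in the 6 months before and one in the 6 months after: no increase. The gap between the two is 4 + (0 to 1) + 5 = 9 to 10 months, longer than the earlier 6-month spacing. The frequency has therefore not risen, and by spacing it has fallen.

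| Definition | Patient 1 | Patient 2 |
|---|---|---|
| 2.1 and 3.1 (analgesics only) | success | success |
| Summary, baseline incidence = historical rate | success | failure |
| Summary, baseline incidence = 3-month entry window (zero for all) | failure | failure |

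Both 6-month scores are taken about one month after an injection. Patient 1's baseline score was taken at least 4 months after one. The gap closes for both patients only in the last row, and no section defines baseline incidence that way.

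**2. The plan's test**

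Inputs from sections 9.2 and 9.5: the null is that the success rate "is no greater than 0.5 against the one-sided alternative hypothesis"; the alternative is 0.75; the significance level is 5%; 40 completers; stated power 80.4% and realized significance level 0.047.

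For N = 40, the smallest r with P(X ≥ r | 40, 0.50) ≤ 0.05 is r = 26. The exact level is 0.0403, and the power at 0.75 is 94.6%. The stated pair does not reproduce at 40. It matches n = 23 with r = 16 (level 0.0466, power 80.4%). The attrition step does reproduce: 40/(1 − 0.20) = 50. The power mismatch is a separate matter and does not affect this point. It does mean that 26/40 is a cut-off derived here and not one the protocol states.

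**3. Illustration of sensitivity**

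Assumptions: the success rate without misattribution is 0.50, and an expected share f of all patients is counted as a success only because of an injection. Then

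P(reach 26/40) = Σ (k = 26 to 40) C(40, k) (0.50 + f)^k (0.50 − f)^(40 − k).

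| Misattributed per 40 | f | P(X ≥ 26) |
|---|---|---|
| 0 | 0 | 4.0% |
| 1 | 0.025 | 7.6% |
| 2 | 0.05 | 13.3% |
| 4 | 0.10 | 31.7% |

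The documents give no value for f. The table shows how sensitive the test is, not how large the bias will be.

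**The case against.** Four arguments deserve an answer.

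- **The Summary may already deal with it.** If baseline incidence means the injection-free entry window, it is zero for everyone, and an injection counted over a like window before month 6 is an increase. That is a fair reading, and the historical rate is no better defined. But 2.1 and 3.1 omit injections altogether, so the Summary reading cannot close the gap alone.
- **Regularly injected patients would often fail anyway.** Take someone kept on an unbroken 4-monthly schedule, last injected 3 to 4 months before the procedure. The next injections fall in months 0 to 1 and 4 to 5: two in the 6 months after against one in the 6 months before. By counts that is an increase, and the Summary rule fails the patient. This stands, and it narrows the affected group under the Summary. It gives no protection under 2.1 and 3.1.
- **Section 4.7.1 allows discontinuation of a participant who newly meets an exclusion criterion.** An injection after the procedure could be treated that way. The clause is discretionary, however, and under sections 4.6 and 4.7.2 a withdrawn patient can be replaced. It would remove the patient rather than score the outcome.
- **Few patients may be affected.** Section 4.1 defines conservative management without mentioning injections. This also stands.

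A reader might infer that the endpoint as a whole can err only in favour of embolization. The documents do not support that: under the Summary, a patient with no injection history who has one injection fails however large the KOOS gain. A reader might also try to put a figure on the inflation of the success rate. That would need an injection prevalence, schedule and effect that the documents do not contain, and it would have to apply the no-increase rule.

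**Conclusion.** The concern holds in a limited form. Baseline and 6-month KOOS are not required to be equally clear of a recent target-knee injection. A patient with earlier injections who is re-injected shortly before month 6 can count as a clinical success under 2.1 and 3.1, and under the Summary if baseline incidence is a historical rate. It cannot be said that every wording allows this, since the zero-baseline reading of the Summary does not.

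For the patients affected, the error is toward success, provided that injections relieve pain at all. Its size is unknown. The move from 4.0% to 7.6% or 13.3% rests on an assumed true rate of 50%, one or two misattributed successes per 40, and the derived 26/40 cut-off. The gap is worth closing because it lies in the primary endpoint, no control arm offsets it and no later SAP is planned to resolve it.

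**What to change.** Use one definition of clinical success in the Protocol Summary and sections 2.1, 3.1 and 9.4.2. It should state that a patient with any ipsilateral intra-articular injection within the 3 months before the 6-month KOOS is scored as not a clinical success, mirroring exclusion 5. Record injection dates with the injection history already taken at visits 5 and 6. As a sensitivity analysis, score any injection between the procedure and the 6-month KOOS as not a success. If a no-increase clause for injections is kept as well, state its look-back period and how injections are counted. Settle this before the preliminary analysis of 10 patients (section 9.4.5), so that the rule is not chosen with outcomes in view.

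The cost is one sentence in four places and a date field. The observed success rate may be slightly lower, because a patient who would have improved anyway but had a late injection is scored as a failure. This is a scoring rule only and does not restrict care.

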1.1 Background Information and Relevant Literature

Knee osteoarthritis (OA) is common and major cause of pain and disability, that affects approximately 12% of Americans aged 60 and above [1]. Its prevalence is rising due to an aging population and the high prevalence of obesity [2]. Radiographically confirmed symptomatic knee OA affects approximately 3.8% of people worldwide, and knee and hip OA ranked as the 11th highest contributor to global disability [3]. Disabling symptoms of knee osteoarthritis are seen in an approximately 10 % of people over 55 years old [4]. Studies have shown that the cost for health services among persons with OA exceeded those without OA by 1.5- to 2.6-fold [1, 5-9]. The first national, population-based study of health care utilization in persons with knee OA shows that knee OA cohort had on average 6.0 more annual MD visits (95% confidence interval [CI]: 4.7, 7.4) and 3.8 more non-MD visits (95% CI: 2.8, 4.7) than the OA-free cohort [1]. This study used the 2003 Medicare Current Beneficiary Survey, a population-based survey of Medicare beneficiaries linked to Medicare claims, we selected a national cohort of community-dwelling persons aged 65 and older with knee OA. Therefore, the prevalence and burden of knee OA presents a major challenge for health systems globally [3].

Knee OA is a complex, multifactorial disease with no known cure. Risk factors for knee OA include joint injury, bone and joint shape, muscle strength and mass, obesity, gender, metabolic factors, nutrition and vitamin factors, bone density, psychological health and occupation [10, 11]. Treatment seeks to manage symptoms, but adequate symptom control can be difficult to achieve [10-12]. Evidence-based treatment options for knee OA include intra-articular corticosteroids, exercise, education, weight management, and oral medications such as acetaminophen and non-steroidal anti-inflammatories for minor symptoms [13]. Total knee arthroplasty (TKA) is reserved for those with severe joint disease, pain and functional limitations, and is an effective intervention for treatment of chronic knee pain and disability in patients with knee OA [14-16]. However, approximately **10% to 44%** of patients experience **persistent chronic pain after TKA** [17, 18], with the highest-quality studies reporting an incidence of approximately 20% [17]. Persistent postsurgical pain is defined as persistent pain of at least three to six months duration that develops or increases in intensity after surgery and affects health-related quality of life [19, 20]. After TKA, patients with persistent pain may be disappointed with the outcome as pain severity plateaus [21-23]. In addition, the economic impact of long-term, moderate-to-severe, and unexplained pain after TKA is profound, particularly in aging population [24].

An in-depth understanding of OA pathophysiology is emerging [2]. Recently, angiogenesis has been implicated in OA by contributing to structural damage, inflammation and pain [25]. Angiogenesis is blood vessel overgrowth from pre-existing vasculature and is essential for growth, development and tissue repair [25]. However, in OA, angiogenesis increases in articular cartilage, synovium, meniscus, and osteophytes, and at the osteochondral junction [26-30]. Because angiogenesis is accompanied by sensory nerve growth, perivascular nerve growth into normally aneural structures such as articular cartilage and meniscus is thought to contribute to OA pain through chemical and mechanical stimulation of newly formed nerves. Modifying angiogenesis and associated nerve growth is a potential treatment pathway to affect the pathogenesis and symptoms of OA [25]. Angiogenesis inhibitor treatment decreased pain-related behavior in animal models [26]. The mechanism of symptomatic relief is unclear but could include reduced synovitis, reduced periarticular innervation and nociception, and maintaining the integrity of the osteochondral junction [25, 26].

While the etiology of persistent pain following TKA is multifactorial [31], there is growing evidence that synovitis and patient-specific inflammatory response to surgery may influence the long-term clinical outcome following TKA [32, 33]. Murakami et al reported that 80% of patients with persistent knee pain following TKA had moderate to severe synovitis compared to only 19% of patients without persistent pain ($p<0.001$) [34]. In a study performed on 46 patients by Kurien T. et al, patients with moderate-to-severe postoperative pain demonstrated higher grades of Hoffa synovitis ($P<0.001$) and knee effusion volume ($P<0.001$) [33]. In OA patients, the extent of synovitis is associated with increased angiogenesis [35]. Nerve growth is linked to angiogenesis in the osteoarthritic joint and has been theorized to be as a potential source of pain in OA patients [25]. Given that removal of the synovium is left to surgeon preference [36], we theorize that unaddressed neovascularity and neural growth may be contributing to persistent post TKA pain.

Over the past decade, GAE has been evaluated for the treatment of knee OA, showing significant improvement in knee pain, function, and quality of life [12, 37-40]. In a study by Okuno et al, The Whole-Organ Magnetic Resonance Imaging Score (WORMS) was evaluated at baseline and at 2 years after embolization in 35 knees and showed

significant improvement of synovitis vs baseline ($P < .0016$) and no osteonecrosis or other evidence indicating aggressive progression of degenerative changes [37]. In an animal study, it's been shown that GAE can limit inflammation in the synovium of OA-affected knees [41]. In a recent abstract accepted as oral presentation during the society of interventional radiology 2023 annual meeting, investigators assessed the efficacy of GAE in this patient population. The preliminary results suggest that GAE in post-TKA patients may be a promising intervention to treat persistent symptoms in this previously challenging patient population [42]. The corresponding study was published in the Journal of Vascular and Interventional Radiology by Taslakian et al. The study reported a clinical success rate of 83% of patients with knee OA post GAE [43].

The goal of this proposed prospective, single-center, single-arm trial is to evaluate the safety and efficacy of GAE for treatment of persistent postsurgical knee pain following TKA.

